2. Definitions of terms and abbreviations

The terms and abbreviations used in this analysis plan are as follows:

Term and abbreviation	Definition
Adverse event	Any untoward or unintended symptoms (including abnormal laboratory findings), condition or illness which are not always related to Humira.
Adverse events in the safety analysis period	Adverse events which occur from the first administration date of Humira through Week 160 of administration (Day 1 + 1120). Note that if a date is not provided, it should also be included in the period for analysis.
Adverse events not in the safety analysis period	Adverse events which occur prior to the first administration date of Humira or beyond Week 160 of administration (Day 1 + 1120).
Adverse reaction	Adverse events for which the causal relation with Humira cannot be ruled out.
Adverse reactions in the safety analysis period	Adverse events which occurred in the safety analysis period and for which the causal relation with Humira cannot be ruled out.
Adverse reactions not in the safety analysis period	Adverse events which occurred not in the safety analysis period and for which the causal relation with Humira cannot be ruled out.
MedDRA/J	Medical Dictionary for Regulatory Activities / Japanese edition
SOC	System Organ Class in MedDRA/J
PT	Preferred Terms in MedDRA/J
LLT	Lowest Level Terms in MedDRA/J
CDAI	Crohn's Disease Activity Index
WPAI	Work Productivity and Activity Impairment Questionnaire : Crohn's Disease
CRP	C-reactive protein
GB	Green book. Guide on re-examination

3. Objective of this statistical analysis plan

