10.2. Safety analysis

Data name	Derivation and calculation methods
Adverse event	
The adverse events for analysis should include not only the events derived from the survey form but also the events covered in the detailed investigation which has been described by the physicians at a contracted site/department even though not derived from the survey form in “Humira CD Long_AE matching list”.
 
With adverse event: at least 1 record on adverse event(s) exists Without adverse event: other than the above.
 
When adverse events are counted per SOC, the identical SOC in a patient should be counted as 1 whereas the same PT in the same patient be counted as 1 for PT. When no applicable patients were observed, display “0” for the number of patients and “0.00” for the percentage.

Seriousness of adverse events	
Based on the seriousness criteria for company assessment which are provided in “Humira CD Long_AE matching list”, regard the events which have been assessed to be serious as serious adverse events.
 
With serious adverse event: at least 1 record on serious adverse event(s) exists Without serious adverse event: other than the above.
 
Follow the way of counting adverse events to count serious adverse

Data name	Derivation and calculation methods
	
events.
 
Give the following priority to serious adverse events for aggregation.
 
[1]serious [2]non-serious

Causal relationship of adverse events	
Unless a serious adverse event is assessed as “not related” in the company causality assessment provided in “Humira CD Long_AE matching list”, regard the event as ‘with’ causal relationship. Give the following priority to causal relationship for aggregation.
 
[1] With causal relationship [2] without causal relationship

Outcome of adverse events	
Use the outcomes for company assessment provided in “Humira CD Long_AE matching list” to give the following priority to the outcomes for aggregation based on the rules in “derivation and calculation methods” for adverse events.
 
[1] [1] death [2] unknown [3] not recovered [4] recovered with sequela [5] recovering [6] recovered [7] not provided

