Days from the first administration date of Humira to the adverse-event onset date	
Use the onset date for company assessment provided in “Humira CD long-term_AE matching list”.
 
When the first administration date of Humira and the adverse-event onset date can be identified as the complete date, they can be used for calculation.
 
When the first administration date of Humira <= the adverse-event onset date:
 
Adverse-event onset date - the first administration date of Humira + 1
 
When the first administration date of Humira > the adverse-event onset date:
 
Adverse-event onset date - the first administration date of Humira
 
When more than one identical PT is found in a patient, use the first onset date to identify the adverse event to be counted.

Days from the adverse-event onset date to the outcome confirmation date (recovered or recovering)	
Use the onset date and the outcomes (recovered or recovering) for company assessment provided in “Humira CD Long_AE matching list”.
 
When the adverse-event onset date and the outcome confirmation date can be identified as the complete date, they can be used for calculation.
 
Outcome confirmation date - adverse-event onset date + 1
 
When more than one identical PT is found in a patient, choose the event which persisted longest until the recovery or the outcome confirmation date.

Data name	Derivation and calculation methods
Incidence of adverse reactions, incidence of serious adverse reactions, incidence of adverse events, incidence of serious adverse events	
Calculate the incidence of adverse reactions, incidence of serious adverse reactions, incidence of adverse events, incidence of serious adverse events with the number of patients with any of the reactions/events in numerator and the number of patients in the safety analysis group in denominator.
 
Provide how to calculate in each table at Chapter 13 and thereafter if other calculation methods are used.

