13.2. Safety

“2.2 A list of the onset status of serious adverse events (Attachment Form 10)”

Patients for analysis: patients in the safety analysis group

Analysis objective: to show the onset status of serious adverse events

Analysis item: aggregate the following items per period for adverse events which occurred in the safety analysis period.

Calculate the number of patients and the percentage to the number of patients surveyed per number of sites surveyed, number of patients surveyed, number of patients with serious adverse events, number of serious adverse events, incidence of adverse events, incidence of serious adverse events and type of adverse reactions, etc. (SOC, PT).

Note: The classification of period should include at approval, cumulative and total.

Put * before the PT of unexpected events from “Precautions”.

“2.3 A list of target-patient summary (Attachment Form 3)”

Patients for analysis: patients whose survey form was locked

Analysis objective: to show a list of patients

Analysis item: provide the items for analysis and the definitions below.

(1) Case number

Provide a serial number starting 1 per patient.

(2) Name of site (company code)

Describe it in Japanese, as the official name. Obtain the name of site from “[CD Long-term]DCF code list_Company A.xlsx” and “[CD Long-term]DCF code list_Company E.xlsx”.

(3) Main establishing entity/code

Obtain the code from “Ultmarc re-examination classification”.

(4) Name of prefecture where the business is located

Fill in the name. Obtain the prefecture's name from “Ultmarc re-examination classification20150731.xlsx”.

(5) Patient abbreviation name

Fill in “not applicable” as mentioned in GB.

(6) Sex

Fill in man, women, unknown or not provided as mentioned in GB.

(7) Date of birth (or age)

Unify it in age. Fill in “A + age + “0000”” as mentioned in GB.

(8) Inpatient/outpatient

Fill in inpatient, outpatient, unknown or not provided as mentioned in GB.

(9) Indication

Code, name of disease: Obtain the MedDRA/J LLT code and LLT from the indication of Humira described in the survey form.

(10) Severity prior to administration

Note: Follow Time Allowance of “12.1 Assessment period for CDAI, WPAI, CRP to show CDAI when the administration was started at the following 4 levels:

<150: remission, ≥ 150 and <220 : mild, ≥ 220 and ≤ 450 : moderate, >450 : severe in severity

(11) Complications

Presence/absence: Refer to the “presence/absence of complications” defined in “10.1 General”.

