Analysis objective: to show the onset status of adverse reactions and serious adverse reactions which occurred not in the follow-up period.

Analysis item: aggregate adverse reactions and serious adverse reactions regarding the following

items based on the adverse reactions which occurred not in the safety analysis period.

Calculate the number of patients and the percentage to the number of patients surveyed per number of patients surveyed, number of patients with adverse reactions, etc. number of adverse reactions, incidence of adverse reactions, etc., and type of adverse reactions, etc. (SOC, PT).

Note: refer to the note of “2.13.1 Incidence of adverse reactions with/without hepatic function disorder and per seriousness” for serious adverse reactions.

Put * before the PT of unexpected events from “Precautions”.

“2.17.3 A list of the onset status of adverse reactions/infections in this survey (patients excluded from the safety analysis)”

Patients for analysis: patients excluded from the safety analysis group

Analysis objective: to show the onset status of adverse reactions and serious adverse reactions.

Analysis item: aggregate adverse reactions and serious adverse reactions regarding the following items based on the adverse reactions which occurred in the safety analysis period.

Calculate the number of patients and the percentage to the number of patients surveyed per number of patients surveyed, number of patients with adverse reactions, etc. number of adverse reactions, incidence of adverse reactions, etc., and type of adverse reactions, etc. (SOC, PT).

Note: refer to the note of “2.13.1 Incidence of adverse reactions with/without hepatic function disorder and per seriousness” for serious adverse reactions.

Put * before the PT of unexpected events from “Precautions”.

“2.19 A list of the onset status of adverse events in this survey”

Patients for analysis: patients in the safety analysis group

Analysis objective: to show the onset status of adverse events, serious adverse events and non-serious adverse events.

Analysis items: aggregate adverse events, serious adverse events and non-serious adverse events regarding the following items among adverse events which occurred in the safety analysis period.

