Calculate the number of patients and the percentage to the number of patients surveyed per number of patients surveyed, number of patients with adverse reactions, number of adverse reactions, incidence of the reactions, type of adverse events (SOC, PT).

Note: refer to the note of “2.13.1 Incidence of adverse reactions with/without hepatic function disorder and per seriousness” for serious adverse events.

“2.20 A list of the onset status of adverse reactions (all cases)”

Patients for analysis: patients in the safety analysis group

Analysis objective: to show the summary statistics on the days to the onset as well as the number of

patients per outcome and the days to the confirmed outcome (recovered or recovering) for adverse reactions.

Analysis items: calculate the number of cases and the percentage to the number of patients in the analysis groups per type of adverse reactions (SOC, PT), the number of patients with non-serious reactions and the percentage to the number of patients in the analysis groups, and the number of patients with serious reactions and the percentage to the number of patients in the analysis groups for the adverse reactions which occurred in the safety analysis period. In addition, calculate the summary statistics (the number of patients, the mean, the minimum, the median, the maximum) for days to the onset per PT, the number of patients per period from the onset date to the outcome (recovered or recovering), and the number of patients per outcome.

Note: When more than one identical PT is found in a patient, aggregate seriousness, days to the onset, outcome and days to the outcome (recovered or recovering) as 1 patient (case) in the following manner.

- Seriousness priority: serious > non-serious
- Days to the onset: identify the days as mentioned in “10.2 days from the first administration date of Humira to the adverse-event onset date”.
- Outcome: identify it as specified in 10.2 Outcomes of adverse events
- Days to outcome (recovered or recovering): identify the days as mentioned in 10.2 Days from an onset date of adverse events to the outcome confirmation date (recovered or recovering).

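### SAP chart 2.19 is meant to tabulate all adverse events of any cause, but its calculation line asks for adverse-reaction totals

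*SAP*

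**What the plan says.** SAP section 2 separates the two terms. An adverse event covers any untoward symptom, "condition or illness which are not always related to Humira". Adverse reactions are the narrower set: "Adverse events for which the causal relation with Humira cannot be ruled out". Section 10.2 takes causality from the company's assessment and names the incidence of each as a separate measure, with "the number of patients with any of the reactions/events in numerator and the number of patients in the safety analysis group in denominator".

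Chart 2.19 in section 13.2 is titled as a list of adverse events. Its objective is "to show the onset status of adverse events, serious adverse events and non-serious adverse events", and its lead-in says to "aggregate adverse events, serious adverse events and non-serious adverse events regarding the following items among adverse events which occurred in the safety analysis period". The calculation line that follows then asks for "number of patients with adverse reactions, number of adverse reactions, incidence of the reactions, type of adverse events (SOC, PT".

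Chart 2.2, the serious adverse event table, mixes the terms the other way round. It asks for the incidence of adverse events and then for "incidence of serious adverse events and type of adverse reactions, etc. (SOC, PT".

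**The concern.** Within one chart, the purpose and the rows are about events while the three totals are about reactions. Under the SAP's own definitions these give different numbers whenever a patient has an event judged not related.

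The protocol (section 9) and SAP section 5.1 both list the occurrence of adverse events as an item separate from the table of adverse reactions, and chart 2.19 is where the full event table is produced. This is a survey without a control group, and causality is taken from the company's assessment. Figures that disregard causality are therefore the reader's check on that judgement. A total that silently applies the causality filter weakens the check in the one table built to provide it.

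**Working it through.** The plan states no figure on this point, so the check is a comparison of the text, followed by an illustration.

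**1. Chart 2.19, element by element**
- Title, objective, lead-in: adverse events, with no causality limit.
- Number of patients, number of occurrences, incidence: adverse reactions.
- SOC/PT rows: adverse events.
- Note on serious cases: serious adverse events.

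Three of the four calculated items disagree with everything around them.

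**2. Could the terms be interchangeable?** No. Section 2 makes reactions a subset of events, and section 10.2 lists the two incidences separately. Section 10.2 also says that a Chapter 13 table states its own calculation where it departs from the general rule, which gives a programmer grounds to follow the line as written.

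**3. Does the SAP change the wording elsewhere?** Yes. Charts 2.4.1.1 and 2.4.1.2 are a reaction/event pair, and the event version switches the term throughout. Chart 2.19 switches only the last item, which suggests text carried over from a reaction chart.

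**4. Which other outputs disregard causality?**
- 2.2: serious events, plus one line for the overall incidence of adverse events.
- 2.4.1.2 and 2.4.2: priority survey items.
- 1.4 and 1.4.1: patient listings, with causality and a safety-group flag.
- 1.4.2 and 1.4.3: listings for deaths and for patients aged 18 or younger.
- 2.4.1.1, 2.5.1 to 2.17.3 and 2.20: reactions.

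No other chart summarises all events by SOC and PT.

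**5. What a literal program would print.** The overall and serious totals would equal those of chart 2.17.1, which has the same population and period. Chart 2.17.1 has no non-serious breakdown, so the overlap stops there. The totals would cover fewer patients than the rows below them. If the overall incidence line in chart 2.2 is computed on events, the report would carry two different overall figures.

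**6. Illustration.** Let *a* be the share of patients with any event and *u* the share of those whose every event was judged not related. The literal total is *a* × (1 − *u*). Both inputs are assumed. N = 500 is the registration target, taken here as the size of the safety group; the percentages do not depend on it.
- *a* = 40%: 500 × 0.40 = 200 patients. With *u* from 10% to 50%, 180 to 100 patients, or 36% to 20%.
- *a* = 60%: 300 patients. Literal total 270 to 150, or 54% to 30%.
- *a* = 80%: 400 patients. Literal total 360 to 200, or 72% to 40%.

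**The case against.** The strongest reply is that this is a slip of terminology and the intended analysis is clear. The title, objective, lead-in, row label and note all say adverse events, and the lead-in governs the items listed after it. A careful programmer would count events, and a literal program would put reaction counts above event rows under an event title, where the mismatch could be seen. That stands: the loss is conditional on a literal reading.

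A reader might go further and infer that the overall incidence regardless of cause is missing from the whole report. The documents do not support that. Chart 2.2 asks for the incidence of adverse events as its own item, and section 10.2 supplies the numerator and denominator. Unrelated events also stay in the SOC/PT rows of chart 2.19 and in listings 1.4 and 1.4.1, from which the count could be rebuilt. For malignant tumour and serious infection, the survey's stated focus, charts 2.4.1.2 and 2.4.2 report events whatever their cause.

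Nor would missing causality data widen the gap. Under section 10.2 an event counts as related unless judged not related "in the company causality assessment provided in" the matching list. That rule is worded for serious events; applying it to non-serious ones is an assumption.

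None of this makes the calculation line correct. It is the operative instruction for the table, and it names the wrong quantity.

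**Conclusion.** The point holds as an internal contradiction in chart 2.19, with a mirror-image slip in the rows of chart 2.2. If programmed literally, the three totals would leave out events judged not related and would disagree with the chart's own rows. If programmed as the surrounding text implies, nothing is lost. The SAP does not say which was done.

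The size cannot be derived, because neither document gives a rate for events or reactions. It equals the share of patients whose only events were judged not related, and the ranges above rest wholly on assumed inputs. The finding is a wording error with a possible effect on one important table. It does not show that the survey fails to report adverse events regardless of cause.

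**What to change.** In SAP section 13.2:
- **Chart 2.19:** replace the three reaction totals with the number of patients with adverse events, the number of adverse events and the incidence of adverse events, each given for all, serious and non-serious events.
- **Chart 2.2:** label the SOC/PT rows as types of serious adverse events.
- **Programs:** check that both tables count events, and that the overall incidence in chart 2.19 agrees with the single line in chart 2.2.

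The cost is a change of SAP wording and a program check. No new data are needed.

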13.3. Effectiveness

“3.1 CDAI remission rate at the final assessment (CDAI<150)”

Patients for analysis: patients in the effectiveness analysis group

Analysis objective: to show the remission rate of CDAI at the final assessment

Analysis items: calculate the number of target patients, the percentage to the number of patients who achieved a remission at the final assessment and to the number of target patients, and the percentage to the number of patients who failed to achieve a remission and to the number of target patients.

Note: Follow “12.1 Assessment period for CDAI, WPAI, CRP and non-intestinal conditions” for Time Allowance of the final assessment periods.

“3.2.1.1 Changes in Crohn’s disease activity index (CDAI) since the administration was started (Observed Case)”

Patients for analysis: patients in the effectiveness analysis group

Analysis objective: to show changes in CDAI and CDAI at each assessment period.

Analysis items: Calculate the number of target patients, the mean and standard deviation of CDAI,

the mean and standard deviation of changes in CDAI for each assessment period, and conduct a paired-t test which compares the values at the initial administration. In addition, calculate the mean days from the first administration date to the final assessment date and the \pm standard deviation.

Note: Follow “12.1 Assessment period for CDAI, WPAI, CRP and non-intestinal conditions” for Time Allowance of the final assessment periods. The analysis covers only the patients with the assessment at the first administration and thereafter.

“3.2.1.2 Changes in Crohn’s disease activity index (CDAI) since the administration was started (Observed Case)”

Patients for analysis: the patients in the effectiveness analysis group whose CDAI was a remission (≥ 150) after they were started on Humira.

Analysis objective: to show changes in CDAI and the CDAI at each assessment period of patients whose CDAI failed to achieve a remission when the administration was started.

Analysis items: Calculate the number of target patients, the mean and standard deviation of CDAI, the mean and standard deviation of changes in CDAI for each assessment period, and conduct a paired-t test which compares the values at the initial administration. In addition, calculate the mean days from the first administration date to the final assessment date and the \pm standard deviation.

Note: Follow “12.1 Assessment period for CDAI, WPAI, CRP and non-intestinal conditions” for Time Allowance of the final assessment periods. The analysis covers only the patients with the assessment at the first administration and thereafter.

“3.2.2.1 Changes in the remission rate at each point (CDAI<150) (Observed Case)”

Patients for analysis: patients in the effectiveness analysis group

Analysis objective: to show the remission rate of CDAI at each assessment period.

Analysis item: Calculate the number of target patients, the percentage to the number of patients who achieved a remission and the number of target patients, 95%CI of the remission rate, and conduct a McNemar test for the first administration per assessment period.

Note: Follow “12.1 Assessment period for CDAI, WPAI, CRP and non-intestinal conditions” for Time Allowance of the final assessment periods. The analysis covers only the patients with the assessment at the first administration and thereafter.

For the confidence interval, use the Clopper-Pearson’s confidence interval.

“3.2.2.3 Changes in the remission rate at each point (CDAI<150) (Observed Case)”

Patients for analysis: the patients in the effectiveness analysis group whose CDAI was a remission (≥ 150) after they were started on Humira.

Analysis objective: to show the remission rate of CDAI at each assessment period of patients whose CDAI failed to achieve a remission when the administration was started.

Analysis item: Calculate the number of target patients, the percentage to the number of patients who achieved a remission and the number of target patients, 95%CI of the remission rate, and conduct a McNemar test for the first administration per assessment period.

Note: Follow “12.1 Assessment period for CDAI, WPAI, CRP and non-intestinal conditions” for Time Allowance of the final assessment periods. The analysis covers only the patients with the assessment at the first administration and thereafter.

For the confidence interval, use the Clopper-Pearson’s confidence interval.

“3.2.4.2 Endoscopy results during administration (small intestine: active phase/remission phase)”

Patients for analysis: patients in the effectiveness analysis group

Analysis objective: to show endoscopy results (small intestine) at each assessment period.

Analysis item: Calculate the number of patients who did not undergo endoscopy, the number of patients who underwent endoscopy, the percentage to the number of patients in the active phase and the number of patients who underwent endoscopy, the percentage to the number of patients in the remission phase and the number of patients who underwent endoscopy, and the mean days from the endoscopy prior to administration to the first administration date of Humira.

Note: Follow “12.2 Assessment period for endoscopy results” for Time Allowance of assessment period. The analysis covers only the patients with the endoscopy assessment (small intestine) at the first administration and thereafter in the effectiveness analysis group.

“3.2.5.2 Endoscopy results during administration (large intestine: active phase/remission phase)”

Patients for analysis: patients in the effectiveness analysis group

Analysis objective: to show the endoscopy results (large intestine) at each assessment period.

Analysis item: Calculate the number of patients who did not undergo endoscopy, the number of patients who underwent endoscopy, the percentage to the number of patients in the active phase and the number of patients who underwent endoscopy, the percentage to the number of patients in the remission phase and the number of patients who underwent endoscopy, and the mean days from the endoscopy prior to administration to the first administration date of Humira.

Note: Follow “12.2 Assessment period for endoscopy results” for Time Allowance of assessment period. The analysis covers only the patients with the endoscopy assessment (large intestine) at the first administration and thereafter in the effectiveness analysis group.

“3.2.5.3 Endoscopy results during administration (remission phase in both small and large intestines)”

Patients for analysis: patients in the effectiveness analysis group

Analysis objective: to show endoscopy results in the remission phase (for small and large intestines)

Calculate the number of patients who underwent endoscopy (for small and large intestines), the number of patients whose small and large intestines in the remission phase, and the percentage to the patients who underwent endoscopy (for small and large intestines).

Note: Follow “12.2 Assessment period for endoscopy results” for Time Allowance of assessment period. The analysis covers only the patients with the data showing that endoscopy for small and large intestines was done on the same day at the first administration and thereafter in the effectiveness analysis group.

“3.2.6.2 Changes in WPAI:CD since the administration was started (Observed Case)”

Patients for analysis: patients in the effectiveness analysis group

Analysis objective: to show WPAI at each assessment period.

Analysis items: Calculate the number of target patients and the summary statistics of WPAI for each assessment period, and conduct a paired-t test which compares the values at the initial administration.

Note: Follow “12.1 Assessment period for CDAI, WPAI, CRP and non-intestinal conditions” for Time Allowance of the final assessment periods. The analysis covers only the patients with the WPAI assessment at the first administration and thereafter in the effectiveness analysis group.

“3.2.7.2 Changes in CRP level since the administration was started (Observed Case)”

Patients for analysis: patients in the effectiveness analysis group

Analysis objective: to show CRP levels at each assessment period.

Analysis items: Calculate the number of target patients and the summary statistics of CRP for each assessment period, and conduct a paired-t test which compares the values at the initial administration.

Note: Follow “12.1 Assessment period for CDAI, WPAI, CRP and non-intestinal conditions” for Time Allowance of the final assessment periods. The analysis covers only the patients with the CRP assessment at the first administration and thereafter in the effectiveness analysis group.

“3.2.7.3 Remission rate at the final assessment in patients who achieved a remission of CDAI at Week 4 of administration”

Patients for analysis: Patients in the effectiveness analysis group (the patients who did not achieve a remission (≥ 150) when the administration was started but achieved the remission (< 150) at Week 4 of administration in CDAI)

Patients for analysis: to show the remission rate of CDAI at the final assessment regarding the patients who did not achieve a remission (≥ 150) when the administration was started but achieved the remission (< 150) at Week 4 of administration.

Analysis items: calculate the number of target patients, the percentage to the number of patients who achieved a remission at the final assessment and the target patients, and the 95% confidence interval of the remission rate.

Note: The target patients need to have their CDAI measured at 3 time points or more, that is, at the first administration, Week 4 of administration and any point after Week 4 of administration and also have a record that they did not achieve a remission (≥ 150) at the first administration but achieved the remission (< 150) at Week 4 of administration.

Follow “12.1 Assessment period for CDAI, WPAI, CRP and non-intestinal conditions” for Time Allowance of the assessment periods.

For the confidence interval, use the Clopper-Pearson's confidence interval.

“3.2.8 Subsequent changes in the conditions of patients with non-intestinal conditions observed at the first administration (Observed Case)”

Patients for analysis: patients in the effectiveness analysis group

Analysis objective: to show the conditions at each assessment period regarding non-intestinal conditions observed at the first administration.

Analysis item: Calculate the number of target patients, the percentage to the number of patients with the conditions and the number of target patients, and conduct a McNemar test for the first administration per assessment period.

Note: The analysis covers only the patients with the assessment at the first administration and thereafter as well as the patients with symptoms for each “arthritis/arthralgia”, “iritis/uveitis”, and “erythema nodosum/gangrenous abscess/aphthous stomatitis” at the first administration.

To analyze “with any of non-intestinal conditions”, the patients with any symptom at each assessment period regarding any of the items answered as ‘with a symptom’ at the first administration are regarded as the patients with conditions. When a patient had multiple symptoms at the first administration, they should be regarded as “with conditions” if any of the symptoms persisted. Do not include in analysis the items in which no symptoms were observed at the first administration. (Do not include in the analysis a symptom which first developed at an assessment

period after the first administration, either)

Follow “12.1 Assessment period for CDAI, WPAI, CRP and non-intestinal conditions” for Time Allowance of the assessment periods.

“3.4.1 Aggregation for effectiveness per patient background factor (CDAI)”

Patients for analysis: patients in the effectiveness analysis group

Analysis objective: to show the CDAI remission rate at the final assessment per patient background factor and analyze them.

Analysis items: For CDAI at the final assessment, calculate the number of patients, the percentage to the number of patients who failed to achieve a CDAI remission and the number of patients per background factor, the number of patients who achieved a CDAI remission and the percentage to the number of patients per background factor, and the tests for CDAI remission (Fisher’s exact test for nominal-scale factors and Man-Whitney’s u test for ordinal-scale factors) per patient background factor below. Note that the test does not include the patients “with treatment history with anti-TNF α drug for Crohn’s disease”.

Note: the patient background factors are as follows:

Sex, age (year), body weight (kg), BMI (kg/m²), duration of illness (year), indication (registration form), allergy history, smoking history, with smoking history (details), self-administration, tuberculosis test status, hepatitis B virus test status (registration form), complication, complication: liver disorder, complication: renal disorder, complication: blood disorder, complication: respiratory disorder, complication: diabetes mellitus, complication: osteoporosis, complication: malignant tumour, medical history, medical history: tuberculosis, medical history: non-tuberculous mycobacteriosis, medical history: interstitial pneumonia, medical history: bronchitis bacterial, medical history: aplastic anaemia, medical history: pancytopenia, medical history: malignant tumour, prior medication for Crohn’s disease, prior medication: anti-TNF α drug, prior medication: aminosalicylic acid drug, prior medication: corticosteroids, prior medication: immunosuppressant, prior medication: antibiotics, prior treatment for Crohn’s disease, prior treatment: surgery, prior treatment: GCAP, prior treatment: enteral nutrition therapy, prior treatment: intravenous nutrition therapy, treatment history with anti-TNF α drug for Crohn’s disease, with treatment history with anti-TNF α drug for Crohn’s disease, concomitant medication, concomitant medication: aminosalicylic acid drug, concomitant medication: corticosteroids, concomitant medication: immunosuppressant, concomitant medication: antibiotics, concomitant therapy for Crohn’s disease, concomitant therapy: surgery, concomitant therapy: GCAP, concomitant therapy: enteral nutrition therapy, concomitant therapy: intravenous nutrition therapy, site of disease: anus/perianal region, site of disease: rectum, site of disease: stomach/duodenum, site of disease: colon, site of disease: jejunum/ileum, intestinal complication, non-intestinal complication, work condition, CDAI when the administration was started, CRP
